5.8.3. Safety Labs.....	22
5.8.4. Vital Sigs.....	22
5.8.5. 12-Lead ECG	23
5.8.6. Physical Exam.....	23
5.9. Other Analyses.....	23
5.9.1. Pharmacokinetic Analyses	23
5.9.2. Pharmacodynamic Analyses	23
5.9.3. Subgroup Analyses	24
5.9.4. Demographics and Baseline Characteristics	24
5.9.5. Medical History	24

CONFIDENTIAL

Statistical Analysis Plan [Version 3.0]

5.9.6.	Concomitant Medications	25
5.9.7.	Compliance	25
5.10.	Interim Analyses	25
6.	References.....	29

CONFIDENTIAL

Statistical Analysis Plan [Version 3.0]

Version History

This Statistical Analysis Plan (SAP) for study B-2660-204 is based on the protocol version 3.0 amendment 2.0, dated May 8th, 2020.

SAP Version	Approval Date	Change	Rationale
1.0	30 August 2020	Not Applicable	Original version
2.0	08 October 2020	Subjects who die or withdraw prior to observing clinical improvement should be censored at Day 28 instead of date of death or withdrawal	Implemented change at the request of FDA. FDA reviewed version 1.0 and provided comments on 22 September, 2020
		All modeling was clarified to indicate that all covariates would be entered into the model at the beginning and the stepwise selection procedure would be used to assess inclusion of these covariates.	
		For all models, corticosteroid use (yes vs no) was added as a potential covariate to include in the stepwise model selection process.	
		In the analysis of the exploratory endpoint of proportion of subjects who are SARS-CoV-2 virus free at Day 10/EOT or hospital discharge, whichever is sooner, subjects who die/withdraw from the study prior to Day 10/discharge will be classified as a non-responder instead of using their last known value.	

CONFIDENTIAL

Statistical Analysis Plan [Version 3.0]

		
For Poisson Regression models, if overdispersion exists, a negative binomial model will be used and a model where the option to adjust the standard errors using the scale parameter will not be run.
	
		
Removed a number of secondary and exploratory efficacy analyses
	
Based on the DSMB recommendation to not expand the study, a number of efficacy analyses were removed to preserve capital

3.0	22 October 2020	
Added additional details on how to derive FiO2 values based on oxygen flow rates.
 
Changed IL-6 sub-group analysis from > ULN to > median,
	
eCRFs collected flow rate or FiO2. Additional details on how to derive FiO2 were needed for programming.
 
IL-6 values do not have normal ranges

1. Introduction

This Statistical Analysis Plan (SAP) contains a more technical and detailed elaboration of the principal features of the analysis described in the protocol and includes detailed procedures for executing the statistical analysis. This SAP should be used in conjunction with the protocol. If there are any discrepancies between the protocol and SAP, this SAP will prevail. Any deviations from this SAP that are implemented in the final analysis will be documented with sound clinical and statistical rationale in the Clinical Study Report (CSR). In the event of any changes to the primary endpoints or analyses, these changes will be documented through a protocol amendment, consistent with ICH E9.

A separate document contains the table, figure and listing specifications and any example programming codes.

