
 Additional efficacy outcomes 	
 Mortality rate during the 28-day study period following enrollment Time to hospital discharge readiness Proportion of subjects ready to be discharged from the hospital during the 28-day study period following enrollment Proportion of subjects with resolution of fever below entry criteria for 24 hours (as defined in Section 5.1.1) by Day 10 in subjects with fever at baseline Time to resolution of fever below entry criteria for 24 hours (as defined in Section 5.1.1) in subjects with fever at baseline Duration (in days) of remdesivir use in subjects starting remdesivir within 24 hours of first dose of BLD-2660 Change from baseline to Days 10, 14, 21 and 28 in clinical status outcome using a 6-point ordinal scale (Section 8.1.3) Proportion of subjects reporting each 6-point ordinal scale of the clinical status outcome assessment Change from baseline to Days 5, 10, 14, 21 and 28 in NEWS score Change from baseline to Days 10, 14, 21 and 28 in IL-6 and D-dimer
Exploratory	

 Other efficacy outcomes 	
 Proportion of subjects who require mechanical ventilation after study entry Number of ventilator-free days to Day 21 Proportion of subjects with ICU transfer and/or ventilator dependence during the 28-day study period following enrollment

Objectives	Endpoints
	
 • The time to a NEWS of ≤ 2 and maintained for 24 hours • Change in NEWS from baseline to Days 3, 5, 8, 10, 14, 21 and 28 in NEWS

 • To evaluate antiviral activity of BLD-2660 in the same population 	
 • Proportion of subjects who are SARS--CoV-2 virus free by Day 10/EOT or hospital discharge, whichever is sooner • Time to eradication of SARS-CoV-2 • Change from baseline in SARS-CoV-2 viral load at Days 5, 10, 14, and 28

 • Other safety outcomes 	
 • Clinically relevant changes from baseline in electrocardiogram (ECG), and clinical laboratory values at each post baseline timepoint • Proportion of subjects with clinically significant drug-related troponin elevations that have repeat elevation upon confirmatory testing as adjudicated by the DMC while continuing on study drug during the 10-day treatment period

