9.4. Statistical Methods

Detailed methodology for summary and statistical analyses of the data collected in this study will be documented in a statistical analysis plan (SAP), which will be maintained by the Sponsor. The SAP may modify the plans outlined in the protocol; however, any major modifications will also be reflected in a protocol amendment. This section is a summary of the planned statistical analyses of the primary and secondary endpoints.

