9.4.2. Efficacy Analyses

The primary efficacy endpoint of time to clinical improvement will be presented using the Kaplan-Meier estimator. Subjects will be censored at Day 28 or earlier, if they discontinue the study prior to observing the event. A Cox proportional hazards model with treatment, remdesivir use (yes/no) and age as covariates will be used to estimate the hazard ratio and compare treatment groups.

The primary efficacy endpoint of change from baseline to Day 10 or hospital discharge if sooner, in the ratio of hemoglobin oxygen saturation to inspired oxygen fraction ($\text{SpO}_2/\text{FiO}_2$) will be analyzed a mixed measures repeated model (MMRM). The Kenward-Roger method will be used to calculate the denominator degrees of freedom for the test of fixed effects and adjusted standard errors. The model will contain treatment, time and the treatment by time interaction as fixed effects and baseline score, age, and remdesivir drug use (yes vs no) as covariates. An unstructured covariance matrix will be assumed to model the within-participant errors.

Sub-group analyses for the two primary endpoints will also be conducted for the following sub-groups: Chloroquine or hydroxychloroquine use (yes vs no), HIV anti-viral drug use (yes vs no) and azithromycin use (yes vs no). If warranted, these effects may be included in the primary model.

No adjustment for multiplicity among the two primary endpoints will be made, as this is a Phase 2 study. Secondary endpoints will be analyzed without adjustment for multiplicity. All efficacy analyses will use the FAS analysis set, and MITT analysis set if applicable.

Secondary endpoints that are defined as time to event endpoints will be analyzed using survival analysis methods. Data will be presented using the Kaplan-Meier. Subjects will be censored at Day 28 or earlier, if they discontinue the study prior to observing the event. A Cox proportional hazards model with treatment, remdesivir use (yes/no), and age as covariates will be used to estimate the hazard ratio and compare treatment groups.

Secondary endpoints that are defined as proportions will be summarized using frequency counts and proportions. Treatment groups will be compared using a Cochran–Mantel–Haenszel (CMH) test stratified by remdesivir use (yes vs no). Additional covariates may be included if warranted.

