10.7. Appendix 7: Protocol Amendment History

Prior Amendments

Blade has introduced the following modifications to Protocol Version 2.0. These changes are presented in order of appearance:

Amendment 1, 23 April 2020

Overall Rationale for the Amendment:

Section # and Name	Description of Change	Brief Rationale
1.1 Synopsis 3.0 Objectives and endpoints	
 Reorganize objectives and endpoints For oxygenation endpoints, added definition for medically fit for removal of oxygen Changed mortality rate to be a secondary endpoint Added Day 28 to relevant endpoints 	
 Per FDA request
1.1 Synopsis 1.2 Schedule of Activities 4.0 Study Design 8.3.1 Time Period and Frequency of Collection of AEs	
 Extended the study follow-up to Day 28 Added 60 days post-study to collect mortality, safety data and forced vital capacity 	
 Per FDA request
5.1.1 Inclusion Criteria	
 Added oxygen requirements inclusion criteria 	
 Per FDA request
5.1.2 Exclusion Criteria	
 Modified supplement oxygen exclusion criteria Added cross reference to the Concomitant Medication section of the protocol Clarified excluded COVID therapies prior to study entry 	
 Based on Investigator's input For clarity and safety measure
6.6 Concomitant Therapy	
 Updated restricted medications section to include azithromycin Clarified to consult with Sponsor's Medical Monitor prior to prescribing chloroquine, hydroxychloroquine and azithromycin Expanded section to include medications affected by potential interactions with BLD-2660 	
 Per FDA request Safety precaution

Section # and Name	Description of Change	Brief Rationale
1.2 Schedule of Activities 8.1.2 Oxygenation Measures	
 Clarified procedures for collecting oxygen saturation 	
 Per Investigator feedback
1.2 Schedule of Activities 8.1.4 Clinical Status Ordinal Score	
 Changed to 6-point ordinal scale by collapsing 'not hospitalized' into 1 category 	
 Per FDA request

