1.1. Objectives and Endpoints

Objectives	Endpoints
Primary	

 To evaluate clinical benefit of BLD-2660 in hospitalized adults with recently diagnosed SARS-CoV-2 infection 	
 Time to recovery as defined by no longer requiring oxygen support or hospital discharge, whichever occurs first

 To evaluate improvement in oxygenation in hospitalized adults with COVID-19 treated with BLD-2660 	
 Change from baseline to Day 10 or hospital discharge, if sooner, in the ratio of peripheral hemoglobin oxygen saturation to fraction of inspired oxygen (SpO₂/FiO₂)
Secondary	

 To evaluate the safety and tolerability of BLD-2660 in the same population 	
 Incidence of TEAEs and serious adverse events (SAEs)

 To evaluate improvement in Biomarkers 	
 Change from baseline to Days 10/EOT, 14, 21 and 28 in serum calprotectin

 Additional efficacy outcomes 	
 Time to hospital discharge readiness Proportion of participants reporting each 6-point ordinal scale of the clinical status outcome assessment Change from baseline to Days 10/EOT, 14, 21 and 28 in IL-6 and D-dimer

Objectives	Endpoints
Exploratory	

 Other efficacy outcomes 	
 Proportion of participants who require mechanical ventilation after study entry

 To evaluate antiviral activity of BLD-2660 in the same population 	
 Change from baseline in SARS-CoV-2 viral load at Days 5, 10/EOT, 14, and 28

 Other safety outcomes 	
 Clinically relevant changes from baseline in electrocardiogram (ECG), and clinical laboratory values at each post baseline time point Proportion of participants with clinically significant drug-related troponin elevations that have repeat elevation upon confirmatory testing as adjudicated by the DMC while continuing study drug during the 10-day treatment period

 To assess population pharmacokinetics (PK) characteristics of BLD-2660 	
 BLD-2660 plasma concentrations

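### SAP v3.0 contains no analysis of the protocol's secondary endpoint of 28-day mortality, and its version history does not name the efficacy analyses that were removed

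*SAP*

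**What the plan says.** Protocol section 3 (and the synopsis) includes among the secondary endpoints "Mortality rate during the 28-day study period following enrollment". The amendment history in section 10.7 gives its origin, "Changed mortality rate to be a secondary endpoint", with FDA request as the rationale. For analysis, section 9.4.2 states "Secondary endpoints that are defined as proportions will be summarized using frequency counts and proportions", followed by a CMH comparison stratified by remdesivir use.

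The SAP's version history for version 2.0 (08 October 2020) records "Removed a number of secondary and exploratory efficacy analyses". Its stated reason is "Based on the DSMB recommendation to not expand the study, a number of efficacy analyses were removed to preserve capital". The items are not listed. SAP 1.1 has no mortality endpoint, and sections 5.5 to 5.9 define no mortality analysis. Mortality is mentioned only in the design description of the 60-day post-study contact (SAP 1.2). On precedence, SAP section 1 says "If there are any discrepancies between the protocol and SAP, this SAP will prevail".

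One retained secondary endpoint has death as a category: "Proportion of participants reporting each 6-point ordinal scale of the clinical status outcome assessment", where score 6 is death (protocol Table 5), reported at Days 10/EOT, 14, 21 and 28 (SAP 5.6.2).

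**The concern.** Because the SAP governs, following it as written produces no mortality endpoint in a trial of hospitalized COVID-19 patients, although the protocol pre-specified one.

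The primary endpoints do not fill the gap. Under SAP 5.5.1, time to clinical improvement takes the first date off oxygen or discharged, so a participant who recovers and later dies counts as a recovery. A death before recovery is censored at Day 28, in the same way as a withdrawal or a participant still on oxygen. For SpO2/FiO2, values absent because of death are handled as missing at random. Protocol mortality was the one efficacy endpoint defined to count deaths by arm.

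At stake is basic benefit-risk information, which also bears on the Phase 3 part described in SAP 5.10. Primary power and type I error are not affected.

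**Working it through.** **1. Endpoint lists side by side.** Protocol section 3 has 5 oxygenation and 10 additional efficacy secondary endpoints: 5 + 10 = 15. SAP 1.1 keeps 3 of them: time to discharge readiness, 6-point scale proportions, and IL-6/D-dimer. Absent: 15 − 3 = 12, of which 28-day mortality is one. SAP 1.1 adds serum calprotectin, which the protocol does not list as an endpoint.

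**2. Can another output stand in?**

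- *Ordinal score 6.* SAP 5.3.1 leaves missing-data rules to each endpoint, and 5.6.2 gives none for death. The SAP 5.2 windows are Day 14 ± 2 = 12–16, Day 21 ± 3 = 18–24 and Day 28 ± 3 = 25–31. A death scored on Day 12 falls in the Day 14 window. Unless score 6 is entered again or carried forward, that participant has no Day 21 or Day 28 value. The CMH test there also compares the whole score distribution, not mortality.
- *Grade 5 TEAE and SAE tables (SAP 5.8.2).* Protocol 8.3.6 treats every death as an SAE. Protocol 10.3.1 excludes expected disease progression from the AE definition, and 10.3.2 says a non-AE cannot be an SAE, giving death from progression as an example. With those rules in conflict, a complete count is not assured.
- *Disposition (SAP 5.4).* Death is a listed withdrawal reason (protocol 7.3), so it appears by arm. Deaths after withdrawal or loss to follow-up can be missed, and there is no interval.
- *Mechanical ventilation (SAP 5.7).* There is no rule for a participant who dies without being ventilated.

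**3. What the endpoint could show.** The documents give no planned mortality figure to reproduce. Protocol 2.2 cites about 14% fatal outcomes (95% CI 6.2–21.5%) in hospitalized patients. Section 5.1.2 excludes patients needing or expected to need ventilation, FiO2 of 0.75 or more, and several comorbidities, so the trial rate may be lower; 3% is added as an assumption. With n = 80 and 40 and a common rate p:

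half-width = 1.96 × √[p(1 − p)(1/80 + 1/40)]

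| p | Deaths in 120 | 95% half-width (points) |
|---|---|---|
| 3% (assumed) | 3.6 | 6.5 |
| 6.2% | 7.4 | 9.2 |
| 14% | 16.8 (11.2 active, 5.6 control) | 13.2 |
| 21.5% | 25.8 | 15.6 |

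At 14%: 1.96 × √(0.14 × 0.86 × 0.0375) = 1.96 × 0.0672 = 0.132.

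Illustration near equal rates: 11/80 against 6/40 is 13.75% − 15.0% = −1.25 points, unstratified Newcombe 95% CI −16.5 to 10.9.

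Power for 28% active against 14% control, two-sided 5%, normal approximation with pooled null variance: pooled rate (22.4 + 5.6)/120 = 0.233; null SE √(0.233 × 0.767 × 0.0375) = 0.0819; alternative SE √(0.28 × 0.72/80 + 0.14 × 0.86/40) = 0.0744; power = Φ[(0.14 − 1.96 × 0.0819)/0.0744] = Φ(−0.28) ≈ 0.39. With the unpooled SE throughout it is Φ(0.14/0.0744 − 1.96) ≈ 0.47.

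**The case against.** The best defence is that deaths are not lost. Score 6 is tabulated by arm at Day 28, and clinical status and survival status are both scheduled then, so a site may well record score 6 for a dead participant. Protocol 8.3.6 is the provision specific to deaths and can be read as overriding the general AE definitions. Disposition gives n (%) of deaths as a discontinuation reason, by arm, with no causality judgement. Precision is poor in any case, and the secondary endpoints carry no multiplicity control.

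Much of this stands. A reader of the report would probably find most deaths. What does not follow is that any of these outputs is a defined 28-day mortality rate with a complete numerator, a rule for unknown vital status and an interval. Low precision argues for estimating rather than testing; it is not a reason to omit the estimate.

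Three stronger readings are tempting, and the documents do not establish them.

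- *Mortality was dropped in version 2.0 to save money.* The removed items are unnamed and version 1.0 was not supplied, so this is an inference.
- *Mortality was dropped because of what the data showed.* SAP 5.10 says the interim that was conducted included efficacy data, but it neither dates that interim nor ties it to the recommendation cited in the version history. The unblinded-team wording, and the list of efficacy endpoints for interim summary, belong to the original interim plan, and that list does not include mortality. Nothing states that the sponsor saw by-arm data. Eleven other secondary efficacy endpoints are also absent, which fits broad trimming.
- *The protocol's amendment rule was breached.* Section 9.4 promises that "any major modifications will also be reflected in a protocol amendment", without defining major; SAP section 1 commits to amendments only for primary endpoints or analyses. Whether this change is major is a judgement.

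**Conclusion.** The omission is a matter of record: the protocol lists 28-day mortality as a secondary endpoint, and the prevailing SAP has no endpoint or analysis for it. The partial substitutes do not provide a complete by-arm rate with an interval, and neither primary endpoint counts all deaths. It should be corrected, as a reporting and benefit-risk gap. It is not a threat to primary power or type I error, and it is not evidence of selective reporting, since the reason mortality is missing cannot be established from these documents.

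Expected size rests on the mortality rate: 7.4 to 25.8 deaths over the protocol's cited range, fewer if the eligibility criteria select lower-risk patients. The half-width of about 13 points assumes 14% in both arms and complete vital status in 80 and 40 participants. The separate table specifications were not supplied and may include a death listing; that would not restore the endpoint.

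**What to change.** - **Endpoint.** Restore 28-day all-cause mortality in SAP 1.1 and 5.6.2. Report n (%) dead by Day 28 by arm in the FAS, the set both documents assign to efficacy, with all randomized participants as support. Take deaths from the survival-status and eCRF death records, and show unknown vital status by arm.
- **Analysis.** Use the remdesivir-stratified CMH comparison of protocol 9.4.2, plus a risk difference with a 95% stratified Newcombe interval, the method SAP 5.7 already uses for mechanical ventilation. Stratify by remdesivir only.
- **Ordinal scale.** State in 5.6.2 that death is carried forward as score 6 at all later visits.
- **Version history.** Name each removed analysis.

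The cost is one endpoint row, one table, one sentence and one list. Survival status is already scheduled at Days 14, 21 and 28 and all deaths go into the eCRF, so no visit, assay or participant is added. The drawback is a wide interval, and the report should say that it is for estimation only and is not evidence of no mortality difference.

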1.1. Objectives and Endpoints

Objectives	Endpoints
Primary	

 To evaluate clinical benefit of BLD-2660 in hospitalized adults with recently diagnosed SARS-CoV-2 infection 	
 Time to recovery as defined by no longer requiring oxygen support or hospital discharge, whichever occurs first

 To evaluate improvement in oxygenation in hospitalized adults with COVID-19 treated with BLD-2660 	
 Change from baseline to Day 10 or hospital discharge, if sooner, in the ratio of peripheral hemoglobin oxygen saturation to fraction of inspired oxygen (SpO₂/FiO₂)
Secondary	

 To evaluate the safety and tolerability of BLD-2660 in the same population 	
 Incidence of TEAEs and serious adverse events (SAEs)

 To evaluate improvement in Biomarkers 	
 Change from baseline to Days 10/EOT, 14, 21 and 28 in serum calprotectin

 Additional efficacy outcomes 	
 Time to hospital discharge readiness Proportion of participants reporting each 6-point ordinal scale of the clinical status outcome assessment Change from baseline to Days 10/EOT, 14, 21 and 28 in IL-6 and D-dimer

Objectives	Endpoints
Exploratory	

 Other efficacy outcomes 	
 Proportion of participants who require mechanical ventilation after study entry

 To evaluate antiviral activity of BLD-2660 in the same population 	
 Change from baseline in SARS-CoV-2 viral load at Days 5, 10/EOT, 14, and 28

 Other safety outcomes 	
 Clinically relevant changes from baseline in electrocardiogram (ECG), and clinical laboratory values at each post baseline time point Proportion of participants with clinically significant drug-related troponin elevations that have repeat elevation upon confirmatory testing as adjudicated by the DMC while continuing study drug during the 10-day treatment period

 To assess population pharmacokinetics (PK) characteristics of BLD-2660 	
 BLD-2660 plasma concentrations

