9.5.1. Data Monitoring Committee

The DMC, a specific independent committee for the study with external representation, will meet when approximately 25%, 50% and 75% of subjects have been recruited and on an ad hoc basis to review safety results. The DMC may recommend stopping the study if at any time during the study there are unacceptable AEs or safety concerns. The members of the DMC will be listed in a separate DMC Charter, the governing document that will supersede this section of the protocol.

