10.5. Appendix 5: Cardiac Monitoring Protocol

All troponin elevations and cardiac AEs and SAEs will be reviewed by the DMC.

Subjects with elevated troponins will be questioned regarding occurrence of any cardiac symptoms. The symptoms will be evaluated by a study investigator and a consulting physician independent of the investigator team who will recommend whether any additional studies should be performed. In addition, during the evaluation period:

1. Study drug could be withheld, at the discretion of the investigator
2. Serum troponin, Creatine Kinase-Myocardial Band (CK-MB), myoglobin, comprehensive metabolic panel (including AST) will be obtained and echocardiogram and ECG performed and interpreted
3. Detailed history of potential causes of troponin elevation should be obtained
4. Additional work up will be initiated per the Investigator's discretion and cardiology consultant

If work up is negative, as determined by Investigator and/or Medical Monitor, no further action is required and, if the study drug had been stopped, it may be restarted.

If work up is positive for a cardiac source, the DMC will review and determine whether the study drug should be permanently discontinued and advise on any next steps, if any.

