5.8.3. Safety Labs

This study will be using local labs instead of central labs. Descriptive summary statistics of the observed values and change from baseline values for hematology, chemistry and urinalysis data at screening, baseline and each post-baseline visit (i.e., Day 5/Discharge, Day 10/Discharge, 14, 21 and 28) will be presented by treatment group. Boxplots will be used to display the distribution of the observed values over time, by treatment group.

Participants with clinically significant values for any safety labs are to be reported as an AE and therefore clinically significant laboratory findings will be interpreted from the AE summaries.

A listing of participants with clinically significant drug-related troponin elevations that have repeat elevation upon confirmatory testing as adjudicated by the DMC while continuing study drug during the 10-day treatment period will be provided.

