5.10. Interim Analyses

[figure not shown]
The study originally planned interim analyses at approximately 25%, 50% and 75% of participants completing the trial. Due to rapid enrollment, only a single interim analysis was conducted, at the time when enrollment had completed (and ~50% of the patients had completed the trial). This interim analysis was not used to stop the trial early for efficacy or futility, as enrollment had already completed, and occurred at a scheduled safety review by the independent

DMC. This interim was for the purpose of ensuring safety and included efficacy data to assess the risk/benefit.

After the last patient has completed their Day 10 assessment, but prior to final data base lock, an interim analysis will be conducted for the purpose of BLADE to begin Phase 3 planning. Blade plans to amend the current protocol to include a second part that would be a Phase 3 trial. As this is a COVID-19 study and there is an immediate public need for effective therapies, BLADE feels amending the protocol to adopt this second Phase 3 part of the study will significantly reduce the start-up time required to initiate the independent phase 3 (part 2 of the study) study by 4-6 months. This approach was communicated to FDA on 11-September 2020, and the sponsor did not receive any objections to this approach. The Phase 3 portion will be analyzed separately from the Phase 2 portion.

The original interim analysis plans for the Phase 2 portion of the study were as follows. An interim analysis is planned when approximately 25%, 50% and 75% of participants have completed the study for the purpose of early stopping for efficacy or futility. Based on the enrollment rates, one or more of these planned interim analyses may occur earlier in time or may not occur at all.

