At the interim analysis when approximately 50% of the participants have completed the study, a sample size re-estimation step will occur using the promising zone approach (Mehta and Pocock, 2011) and method of Chen, DeMets and Lan, based on the observed effect size at this interim analysis. The promising zone is defined as a conditional power of between 50% and 80%. If the conditional power falls into this region the sample size may be increased to raise the conditional power to 80%.

CONFIDENTIAL

Statistical Analysis Plan [Version 3.0]

The study will not stop enrolment awaiting these DMC reviews, though the DMC may recommend temporary or permanent cessation of enrolment based on their safety reviews.

A separate unblinded statistical team will prepare the above information for the DMC to review and make recommendations to the Sponsor. The following efficacy endpoints will be summarized at each interim analysis using the FAS:

Objectives	Endpoints
Primary	

 To evaluate clinical benefit of BLD-2660 in hospitalized adults with recently diagnosed SARS-CoV-2 infection 	
 Time to recovery as defined by no longer requiring oxygen support or hospital discharge, whichever occurs first

 To evaluate improvement in oxygenation in hospitalized adults with COVID-19 treated with BLD-2660 	
 Change from baseline to Day 10 or hospital discharge, if sooner, in the ratio of peripheral hemoglobin oxygen saturation to fraction of inspired oxygen (SpO₂/FiO₂)
Secondary	

 	

 Additional efficacy outcomes 	
 Time to hospital discharge readiness
Exploratory	

 Other efficacy outcomes 	
 Proportion of participants who require mechanical ventilation after study entry

6. References

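### The only troponin endpoint is filtered on relatedness and delivered as a listing, so the SAP requires no attribution-free count of confirmed troponin elevations by arm

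*SAP*

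**What the plan says.** The endpoint appears among the exploratory other safety outcomes in Protocol section 3 and SAP 1.1: "Proportion of participants with clinically significant drug-related troponin elevations that have repeat elevation upon confirmatory testing as adjudicated by the DMC". It is restricted further to patients who stay on study drug during the 10-day treatment period.

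The planned output is in SAP 5.8.3: "A listing of participants with clinically significant drug-related troponin elevations", under the same conditions. The descriptive summaries by treatment group in that section name hematology, chemistry and urinalysis.

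Protocol Appendix 5 gives the DMC a wider remit than the endpoint does: "All troponin elevations and cardiac AEs and SAEs will be reviewed by the DMC". It also gives the DMC a case-level role: "If work up is positive for a cardiac source, the DMC will review and determine whether the study drug should be permanently discontinued".

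On what the DMC receives, SAP 5.10 says: "A separate unblinded statistical team will prepare the above information for the DMC to review and make recommendations to the Sponsor". Of the interim that was held, it says: "This interim was for the purpose of ensuring safety and included efficacy data to assess the risk/benefit". Protocol 9.5.1 leaves DMC operation to a charter that is not among the documents: "The members of the DMC will be listed in a separate DMC Charter, the governing document that will supersede this section of the protocol".

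**The concern.** Relatedness to study drug is part of the outcome definition. In a randomized placebo-controlled trial that judgement is unnecessary, because an excess in the active arm over the placebo arm is itself the evidence of a drug effect. Case-by-case attribution cannot add events. It removes some, and in patients whose illness offers a competing explanation it may remove many.

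The endpoint is named as a proportion but delivered as a listing, which has no denominators and omits every confirmed elevation judged unrelated. A reader of the final report could not compare the arms on confirmed troponin elevation from what the SAP requires.

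This matters because elevated troponin is the only entry in the risk table (Protocol 2.3.1) and has its own monitoring appendix, and because SAP 5.10 says the trial will feed Phase 3 planning. The data already exist: the Schedule of Activities has serum troponin at baseline, daily in treatment, and on Days 10, 14, 21 and 28.

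**Working it through.** **Step 1: is there another route to an unfiltered count by arm?**

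| Possible source | What it gives | Gap |
|---|---|---|
| SAP 5.8.3 listing | Adjudicated drug-related cases | No denominators; unrelated cases absent |
| SAP 5.8.3 summaries by arm | Hematology, chemistry, urinalysis | Protocol Table 8 puts troponin outside all three, under other assessments |
| Protocol 9.4.3 | Laboratory evaluations by treatment, in general terms | SAP section 1 says the SAP prevails where the two differ |
| SAP 5.8.2 adverse event tables | Events by arm regardless of relationship | Protocol 10.3.1 excludes abnormal findings associated with the underlying disease unless worse than expected, which is a second attribution filter |
| Separate table specifications (SAP section 1) | Unknown | Not among the documents; the SAP text does not require the table |

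None of the available texts requires the count.

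**Step 2: what the filter does.** The plan states no rate, sample size or power for this endpoint, so there is no figure to reproduce. Arm sizes are 80 and 40 (SAP section 3). Let p be the true rate of confirmed elevation and f the fraction called drug-related; both are assumptions. The expected counts are 80 × p × f (active) and 40 × p × f (placebo).

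With no drug effect (the same p in both arms), active versus placebo:

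| | p = 5% | p = 10% | p = 20% |
|---|---|---|---|
| All confirmed elevations | 4 v 2 | 8 v 4 | 16 v 8 |
| f = 0.5 in both arms (masked) | 2 v 1 | 4 v 2 | 8 v 4 |
| Chance of no placebo case under masked f = 0.5, (1 − p × f)^40 | 36% | 13% | 1.5% |
| f = 0.5 active, 0 placebo (allocation known) | 2 v 0 | 4 v 0 | 8 v 0 |
| Spurious risk difference in that case | 2.5 points | 5 points | 10 points |
| f = 1 active, 0 placebo | 4 v 0 | 8 v 0 | 16 v 0 |
| Spurious risk difference in that case | 5 points | 10 points | 20 points |

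If every case is attributed to COVID-19 (f = 0 in both arms), the result is 0 v 0 whatever the drug does.

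With a true effect and masked attribution, a risk difference D appears as f × D. For example, 20% versus 10% is 16/80 versus 4/40. At f = 0.5 it becomes 8/80 versus 2/40, or 10% versus 5%, so a 10-point difference is shown as 5 points.

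**Step 3: what the missing table would offer.** At 10% in both arms, the standard error of the difference is √(0.10 × 0.90/80 + 0.10 × 0.90/40) = √0.003375 = 0.058. The 95% interval is about ±1.96 × 0.058, or ±11 points. That is wide, but it is not distorted by attribution.

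**The case against.** A reader might infer that the DMC adjudicates with individual assignments in view, so that the placebo count is near zero by construction. The documents do not support that. SAP 5.10 shows that the DMC receives comparative interim information from an unblinded team. It does not say that members know a patient's allocation when they review a troponin case, and operating rules are left to the charter. Nor is it settled that the DMC assigns relatedness: Protocol 10.3.3 gives causality to the investigator in a double-blind study, and the DMC may only confirm the repeat elevation. On that reading placebo cases can count. The allocation-known rows above are therefore conditional.

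It is also fair to say that the endpoint is exploratory, that SAP 5.8 makes all safety analyses descriptive, and that a listing cannot by itself produce a between-arm difference. Even 4/80 versus 0/40 has a one-sided Fisher p-value of only about 0.19, for a test the plan does not contain. SAP 5.8.3 does send clinically significant laboratory values to the adverse event tables, which are by arm and include unrelated events.

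All of that stands. It limits the point without removing it. The adverse event route has its own attribution filter, and neither the lost events nor the missing table depends on whether adjudication was masked.

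**Conclusion.** The concern holds as a reporting gap. For the one risk the protocol identifies, the SAP requires only a listing of attributed cases and no count of confirmed elevations by arm. Even masked attribution shrinks a real difference in proportion to the fraction attributed; at an assumed one half, 10 points become 5.

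Non-comparability of the arms would follow only if the adjudicators knew allocation. The documents are silent on that, so it is a reason to state the masking and not a finding that the endpoint is biased. All rates and attribution fractions here are assumptions. No efficacy conclusion and no planned test is affected. The change is worth making before database lock because the data are in hand and it costs almost nothing.

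**What to change.** - In SAP 5.8.3, add a table of all repeat-confirmed post-baseline troponin elevations by treatment arm, as n/N with a confidence interval, regardless of attribution. It needs a stated rule for what counts as an elevation and as a repeat, since neither document gives a threshold.
- Keep the DMC-adjudicated drug-related cases as a supplementary listing.
- State in the SAP or charter that any adjudication of relatedness or clinical significance for this endpoint is made masked to treatment, and who makes it. If cases have already been adjudicated, record whether that was masked.

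Leave the Appendix 5 clinical pathway and the DMC's safety role unchanged. Moving adjudication to the person whom Appendix 5 describes as "a consulting physician independent of the investigator team who will recommend whether any additional studies should be performed" is not proposed: it would alter a clinical pathway, and nothing shows that the role is masked or staffed for endpoint review.

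The cost is one extra descriptive table and a line of SAP or charter wording. No new tests or visits are needed.
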